- 16. Patients who have taken herbal medications and certain fruits within 7 days prior to starting study drug. Herbal medications include, but are not limited to St. John's Wort, Kava, and ephedra (ma huang), dehydroepiandrosterone (DHEA), gingko biloba, yohimbe, saw palmetto, and ginseng. Fruits include the CYP3A inhibitors Seville oranges, grapefruit, pummelos, or exotic citrus fruits.
- 17. Patients who are currently treated with drugs known to be moderate and strong inhibitors or inducers of isoenzyme CYP3A, and the treatment cannot be discontinued or switched to a different medication prior to starting study drug. Please refer to Table 15 for a list of prohibited inhibitors and inducers of CYP3A (Please note that co-treatment with weak inhibitors of CYP3A is allowed).
- 18. Patients who have received chemotherapy or targeted anticancer therapy ≤ 4 weeks (6 weeks for nitrosourea, antibodies or mitomycin-C) prior to starting study drug must recover to a Grade 1 before starting the trial
- 19. Patients who have received any continuous or intermittent small molecule therapeutics (excluding monoclonal antibodies) ≤ 5 effective half-lives prior to starting study drug or who have not recovered from side effects of such therapy
- 20. Use of statin drugs or other medications known to associate with rhabdomyolysis. These drugs must be discontinued at enrollment.

- 21. Patients who have received wide field radiotherapy ≤ 4 weeks or limited field radiation for palliation ≤ 2 weeks prior to starting study drug or who have not recovered from side effects of such therapy
- 22. Patients who have undergone major surgery ≤ 2 weeks prior to starting study drug or who have not recovered from side effects of such therapy.
- 23. Patients who are currently taking therapeutic doses of warfarin sodium or any other coumadin-derivative anticoagulant. Low molecular weight heparin is allowed.

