4.1.2.3.2 Guidelines for the treatment of study drug induced stomatitis/ oral mucositis

General guidance and management include patient awareness and early intervention. Evaluation for herpes virus or fungal infection should be considered.

Patients should be informed about the possibility of developing mouth ulcers/ oral mucositis and instructed to report promptly any signs or symptoms to their physician, Patients should be educated about good oral hygiene, instructed to avoid spicy/acidic/salty foods, and should follow the following guidelines:

- ◆◆ For mild toxicity (Grade 1), use conservative measures such as non-alcoholic mouth wash or salt water (0.9%) mouth wash several times a day until resolution.
- For more severe toxicity (Grade 2 in which case patients have pain but are able to maintain adequate oral alimentation, or Grade 3 in which case patients cannot maintain adequate oral alimentation), the suggested treatments are topical analgesic mouth treatments (ie, local anesthetics such as benzocaine, butyl aminobenzoate, tetracaine hydrochloride, menthol, or phenol) with or without topical corticosteroids, such as triamcinolone oral paste 0.1% (Kenalog in Orabase[®]), or as per local practice.
- ◆◆ Agents containing alcohol, hydrogen peroxide, iodine, and thyme derivatives may tend to worsen mouth ulcers. It is preferable to avoid these agents.

Antifungal agents should be avoided unless a fungal infection is diagnosed as they may interfere with buparlisib metabolism. Oral or systemic liver enzyme inhibitors such as topical antifungal creams are allowed.

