4.2 Treatment Administration

4.2.1 Buparlisib Administration

The study drug buparlisib will be self-administered (by the patients themselves). The investigator will instruct the patient to take the study drug exactly as specified in the protocol. Buparlisib will be administered on a continuous once daily dosing schedule at a dose of **80mg daily**. Patients should be instructed to take the dose of buparlisib with Sonidegib (see below) daily in the morning, two hours after a light breakfast (morning meal) at approximately the same time each day. Buparlisib should be taken with a glass of water and consumed over as short a time as possible. Patients should swallow the capsules as a whole and not chew them. Do not crush capsule. Patients should continue to fast for 2 hours after the administration of each buparlisib dose.

If vomiting occurs during the course of treatment, no re-dosing of the patient is allowed before the next scheduled dose. The occurrence and frequency of any vomiting during a treatment cycle must be noted as an adverse event. If the patient forgets to take her/his dose before 6:00 PM, then the dose should be withheld that day and buparlisib should be restarted the following day.

Patients must avoid consumption of St John's Wort, Seville oranges, grapefruit or grapefruit juice, grapefruit hybrids, pummelos and exotic citrus fruits from 7 days prior to the first dose of study medication and during the entire study treatment period due to potential CYP3A4 interaction with the study medication. Patients must avoid concomitant intake of strong and moderate CYP3A4/5 inhibitors and inducers. Orange juice is allowed. All dosages prescribed and dispensed to the patient and all dose changes during the study must be recorded. If a patient requires a buparlisib dose delay of > 21 days from the previous dose, the patient must be discontinued from treatment completely and will only require a 28-day follow up visit for study completion.

Medication labels will comply with US legal requirements and be printed in English. They will supply no information about the patient. The storage conditions for study drug will be described on the medication label.

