4.2.3 Concomitant therapy

All medications (excluding prior chemotherapy and biologic, immunologic or radiation therapy) taken within 4 weeks prior to the administration of buparlisib/sonidegib and all concomitant therapy administration during the study with reasons for therapy should be recorded. All prior chemotherapy; biologic, immunologic or radiation therapy; and surgery within 4 weeks prior to the administration of study drug, will be recorded.

Patients on chronic medications that can be given concomitantly with buparlisib/ sonidegib should be maintained on the same dose and dose schedule throughout the study period, as medically feasible. The investigator should instruct the patient to notify the study site about any new medications he/she takes after the start of the study drug. All medications (other than study drug) and significant non-drug therapies (including herbal medicines, physical therapy and blood transfusions) administered after the patient starts treatment with study drug, and any changes in dosing should be recorded.

In general, the use of any concomitant medication/therapies deemed necessary for the care of the patient is permitted with the following exceptions described below in Section

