4.2.3.1 Drugs that are prohibited

- ♦♦ Other investigational therapies must not be used while the patient is on the study.
- ◆◆ Anticancer therapy (chemotherapy, biologic or radiation therapy, and surgery) other than the study treatments must not be given to patients while the patient is on the study. If such agents are required for a patient then the patient must be discontinued from the study.
- ♦ In vitro metabolism studies suggest that oxidative metabolism of buparlisib is predominantly mediated by CYP3A4 (fm>0.9), with only minor contributions of CYP1A1. As buparlisib is a sensitive CYP3A4 substrate, co-administration of buparlisib with strong and moderate CYP3A4 inhibitors and CYP3A4 inducers is prohibited. Refer to Table 15 for a list of prohibited drugs. Please note this list may not be comprehensive.
- Based on in vitro studies, co-administration of buparlisib with CYP3A4 inducers is predicted to decrease the systemic exposure to buparlisib, thereby increasing the risk of exposing the patient to subtherapeutic drug levels. Refer to Table 15 for a list of prohibited CYP3A inducers. Please note that this list may not be comprehensive. Therapeutic doses of warfarin sodium (Coumadin®) or any other coumadin-derivative anticoagulants are not permitted.
- •• If a patient requires the concomitant use of any medication included in Table 16 entitled "List of Prohibited QT prolonging drugs" (ie, drugs that are generally accepted by the Qtdrugs.org Advisory Board of the Arizona CERT to have a risk of causing Torsades des de Pointes), study treatment administration must be interrupted as long as the patient requires therapy with the QT prolonging agent.
- ♦♦ Herbal preparations/medications are not allowed throughout the study. These herbal medications include, but are not limited to St. John's wort, Kava, ephedra (ma huang), ginko biloba, dehydroepiandrosterone (DHEA), yohimbe, saw palmetto, ginsing. Patients should stop using these herbal medications 7 days prior to first dose of study drug.

◆◆ Hormonal contraceptives may be affected by cytochrome P450 interactions, and are therefore not considered effective in this study.

Table 15. List of prohibited CYP3A Inhibitors and Inducers

СҮРЗА	Inhibitors	СҮРЗ	3A Inducers
Strong	Moderate	Strong	Moderate

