clarithromycin conivaptan grapefruit juice Indinavir itraconazole ketoconazole Lopinavir Mibefradil nefazodone Nelfinavir posaconazole Ritonavir Saquinavir	aprepitant atazanavir cimetidine ciprofloxacin darunavir diltiazem erythromycin fluconazole tofisopam verapamil amprenavir fosamprenavir elvitegravir tipranavir	avasimibe carbamazepine Phenobarbital (barbiturate) phenytoin rifabutin rifampin St John's Wort	bosentan efavirenz etravirine modafenil nafcillin ritonavir talviraline tipranavir
telithromycin troleandomycin voriconazole			

This database of CYP inhibitors was compiled from the Indiana University School of Medicine's "Clinically Relevant" Table and from the University of Washington's Drug Interaction Database based on *in vitro* studies. Strong inhibitors are predicted to increase buparlisib AUC > 5-fold, and moderate inhibitors are predicted to increase buparlisib AUC ≥ 2-fold but < 5-fold.

This database of CYP inducers was compiled from the FDA's "Guidance for Industry, Drug Interaction Studies;" from the Indiana University School of Medicine's "Clinically Relevant" Table; and from (Pursche *et al.* 2008).

All QT-prolonging drugs listed in Table 4-8 are prohibited for all patients from screening through permanent discontinuation of study treatment. Table 16 below lists drugs with a known risk for Torsades de Pointes (TdP) as well as sensitive CYP3A substrates (with narrow TI) with a possible or conditional risk for TdP.

Table 16. List of prohibited QT-prolonging drugs

Drug	QT risk(*)	Comment
Amiodarone	Known risk for TdP	Females > Males, TdP risk regarded as low
Arsenic trioxide	Known risk for TdP	
Astemizole	Known risk for TdP	No Longer available in U.S.
Bepridil	Known risk for TdP	Females>Males
Chloroquine	Known risk for TdP	
Chlorpromazine	Known risk for TdP	
Cisapride	Known risk for TdP	Restricted availability; Females > Males.
Disopyramide	Known risk for TdP	Females > Males
Dofetilide	Known risk for TdP	
Domperidone	Known risk for TdP	Not available in the U.S.
Droperidol	Known risk for TdP	
Halofantrine	Known risk for TdP	Females>Males
Haloperidol	Known risk for TdP	When given intravenously or at higher-than- recommended doses, risk of sudden death, QT prolongation and torsades increases.
Ibutilide	Known risk for TdP	Females>Males
Levomethadyl	Known risk for TdP	
Mesoridazine	Known risk for TdP	
Methadone	Known risk for TdP	Females > Males
Pentamidine	Known risk for TdP	Females > Males
Pimozide	Known risk for TdP	Females > Males

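### One sentence, in the stomatitis guidance (4.1.2.3.2) and in the note to exclusion 15, reads as permission for oral or systemic enzyme inhibitors that 4.2.3.1 and Table 15 prohibit

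*Combined protocol and SAP*

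**What the plan says.** Section 4.1.2.3.2 advises considering an evaluation for viral or fungal infection in a patient with mouth ulcers. It then says: "Antifungal agents should be avoided unless a fungal infection is diagnosed as they may interfere with buparlisib metabolism". The next sentence is: "Oral or systemic liver enzyme inhibitors such as topical antifungal creams are allowed". The same sentence stands in section 3.2.2.2, in the note to exclusion 15 on steroids and immunosuppressants.

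Elsewhere the rule runs the other way:

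- Exclusion 17 covers "Patients who are currently treated with drugs known to be moderate and strong inhibitors or inducers of isoenzyme CYP3A" when the drug cannot be stopped or switched. It expressly leaves weak CYP3A inhibitors allowed.
- Section 4.2.1: "Patients must avoid concomitant intake of strong and moderate CYP3A4/5 inhibitors and inducers".
- Section 4.2.3: "the use of any concomitant medication/therapies deemed necessary for the care of the patient is permitted with the following exceptions". Those exceptions follow in 4.2.3.1.
- Section 4.2.3.1: "co-administration of buparlisib with strong and moderate CYP3A4 inhibitors and CYP3A4 inducers is prohibited".
- Table 15 lists the prohibited drugs. Its strong-inhibitor column contains the run "itraconazole ketoconazole Lopinavir Mibefradil nefazodone Nelfinavir posaconazole Ritonavir Saquinavir" and also voriconazole. Fluconazole is in the moderate column.
- Appendix B, exclusion items 12 and 17, repeats the restriction in the eligibility checklist.

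**The concern.** A sentence that declares oral or systemic enzyme inhibitors acceptable, with no limit on enzyme or strength, cannot stand beside a ban on strong and moderate CYP3A inhibitors. The place that matters is 4.1.2.3.2, because a clinician treating a sore mouth on study drug would look there. The local text warns about antifungals, relaxes the warning once an infection is diagnosed, and then reads as permission. Nothing there refers to Table 15 or 4.2.3.1.

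At stake is buparlisib exposure in a patient given a listed azole. Section 4.2.3.1 calls buparlisib a sensitive CYP3A4 substrate. Sonidegib is also cleared mainly by CYP3A4 (1.4.1.1.1), and section 1.4.7.1 links higher sonidegib AUC to higher odds of dose-limiting CK elevation. The documents give no fold-change for sonidegib with an inhibitor, so that part is not quantified.

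**Working it through.** **Text comparison.**

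1. The general term in the sentence is oral or systemic inhibitors, but its only example is a topical cream. The example is not a member of the class, so the sentence cannot be correct as written.
2. If the general term governs, every oral or systemic inhibitor is allowed. That overlaps with the ban for strong and moderate CYP3A inhibitors, and Table 15 names five azoles in the overlap: itraconazole, ketoconazole, posaconazole and voriconazole (strong), and fluconazole (moderate). For weak CYP3A inhibitors there is no conflict.
3. If the example governs, only topical products are allowed and nothing conflicts. Section 4.1.2.3.4 fits this reading: it recommends topical erythromycin for mild acneiform rash, although Table 15 lists erythromycin as a moderate inhibitor.
4. In the note to exclusion 15 the sentence does not override exclusion 17, which follows shortly after and is specific. In 4.1.2.3.2 no such rule stands nearby.

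**Size of the exposure effect if a listed azole were given.** The plan gives no ratio to the MTD, so there is no figure to reproduce. The inputs are:

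- Study dose of buparlisib: 80 mg daily (1.5.2.2.4, 4.2.1).
- Single-agent MTD: 100 mg daily (1.5.2.2.1).
- AUC approximately dose-proportional over 12.5 to 150 mg (1.5.2.1). The scaling needs this only between 80 and 100 mg, both inside the range.
- Predicted fold-rise F in buparlisib AUC (note to Table 15): at least 2 but under 5 for moderate inhibitors, over 5 for strong ones.
- Assumption: sonidegib does not change buparlisib AUC.

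Mean AUC at 80 mg with the inhibitor, relative to the mean at 100 mg alone, is F × 80/100.

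| Inhibitor | F | F × 0.8 |
|---|---|---|
| Moderate, lower bound | 2 | 1.6 |
| Moderate, upper bound (not reached) | 5 | 4.0 |
| Strong | over 5 | over 4.0 |

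These ratios describe co-administration. They say nothing about how likely this sentence is to cause it.

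**The case against.** The strongest reply is that the matter is already settled. The prohibition appears in exclusion 17, 4.2.1, 4.2.3.1, Table 15 and two checklist items, and 4.2.3 makes all concomitant medication subject to it. The preceding sentence in 4.1.2.3.2 names no azole and can be read together with the ban: a diagnosed infection may be treated with an agent not listed in Table 15. Relaxing a general caution does not repeal a named prohibition, and the same sentence tells the prescriber that metabolism is the concern.

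Most of this stands, and it is why the severity is low. A reader might infer that the protocol lacks a rule on systemic azoles, or that it authorises them. The documents do not support either reading, because the rule is explicit and the sentence's only example is topical. What the reply does not remove is that the sentence is wrong as written, in operative text, at the point where an antifungal may be chosen, and with no cross-reference to the list that governs the choice.

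**Conclusion.** The point holds as a low-severity safety wording correction. The sentence contradicts itself and, taken literally, conflicts with the CYP3A ban. The practical exposure is one situation: a diagnosed oral fungal infection during treatment. If a listed azole were then given, mean buparlisib AUC at 80 mg would be 1.6 to under 4.0 times (moderate), or over 4.0 times (strong), the mean at the 100 mg single-agent MTD. This rests on the protocol's own predicted fold-rises, approximate dose proportionality, and no sonidegib effect on buparlisib.

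Two further inferences are tempting and unsupported. The first is a statement about individual patients, for example whether someone with low exposure would still pass the mean MTD AUC at a 2-fold rise. Between-patient variability is given as around 40% in general (1.5.2.1) and about 36% for systemic exposure at 100 mg (1.5.2.2.2). One SD below the mean gives 0.60 × 1.6 = 0.96 with the first figure and 0.64 × 1.6 = 1.02 with the second, so the answer turns on which is used. Only the mean ratios should be relied on. The second is a frequency. Section 4.3.3 reports mucosal inflammation in 18.2% of patients on buparlisib, but that is not a rate of fungal infection, and the documents give no basis for estimating how often the sentence would lead to azole use.

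**What to change.** In both 4.1.2.3.2 and the note to exclusion 15, replace the sentence with: *Topical antifungals are allowed; oral or systemic moderate or strong CYP3A inhibitors, including the azole antifungals listed in Table 15, are prohibited (see 4.2.3.1).* Weak CYP3A inhibitors stay allowed under exclusion 17.

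Optionally, in 4.1.2.3.2 only, say what to do if a listed azole is medically necessary. Section 4.2.3.1 already has a model for prohibited QT-prolonging drugs: "study treatment administration must be interrupted as long as the patient requires therapy with the QT prolonging agent". It states no equivalent for CYP3A inhibitors. Any added text should interrupt study treatment, which section 5.1 defines as both drugs. Stopping buparlisib alone would leave sonidegib, itself a CYP3A4-cleared drug, running alongside the azole. The interruption should stay subject to the existing rule in 4.1.1 and 4.2.1 that a delay of more than 21 days leads to discontinuation.

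The cost is one sentence reworded in two places, plus the optional addition. Endpoint, sample size and analysis are untouched.

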4.1.2.3.3 Guidelines for the Treatment of Buparlisib-induced Psychiatric Disorders

Psychiatric adverse events will be closely monitored and evaluated at each planned visit until recovery to Grade ≤ 1 or baseline status. The grading of psychiatric adverse events/mood alterations must be based on the clinical interpretation of severity according to the NCI-CTCAE (v 4.03) guidelines.

For patients who experience new or worsening of existing psychiatric AEs of Grade ≥1, psychiatric consultation should be considered as described in Table 10.

Patient self-reported mood questionnaires (GAD-7 and PHQ-9) will be used for screening and during the study treatment phase to aid the investigator in identifying new or worsening of events. For additional information regarding safety assessments based on patient self-reported mood questionnaires, please refer to Section Patient self rating mood questionnaires.

If question 9 in the PHQ-9 has a positive response (as indicated by selecting "1", "2", or "3"), omit treatment with buparlisib and refer the patient for psychiatric consultation for optimal management regardless of the total questionnaire score or CTCAE grading to confirm if study drug should be interrupted or permanently discontinued. In this specific case, the psychiatric advice can overrule the patient's PHQ-9 self-assessment. During the study, subjects will be monitored at regular scheduled visits (eg, Day 15 of Cycle 1, Day 1 and Day 15 of Cycles 2, Day 1 of each subsequent cycle, and at the End of Treatment visit) by the investigator/site staff through personal interaction and the two self reported questionnaires. Additional assessments may be done according to the clinical judgment of the investigator if desired.

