	For non-fasting plasma glucose > 500 mg/dL (> 27.8 mmol/L) accompanied by signs/symptoms of hyperglycemia (for example, mental status changes, excessive thirst, polyuria), or presence of blood or urine ketones, discontinue buparlisib and following guidance for management of Grade 4 fasting plasma glucose (FPG).
	Cardiac
Cardiac - Left Ventricular systolic dysfunction	
Grade 1 or 2 Asymptomatic, resting ejection fraction 40-50%; or 10-20% drop from baseline	Reduce buparlisib dose by 50% Repeat LVEF within 4 weeks or as clinically appropriate
Table 10. Recommended dose modifications and dose delays for suspected buparlisib** treatment-related toxicities	
Worst toxicity CTCAE grade* (value)	During a cycle of therapy
Grade 3	Discontinue buparlisib
Symptomatic, ejection fraction responsive to intervention, ejection fraction 20-39% or > 20% drop from baseline	LVEF measurement to be repeated within 4 weeks or as clinically appropriate

Grade 4	Discontinue buparlisib
Refractory or poorly controlled heart	Hospitalize if appropriate
failure due to drop in ejection fraction;	Trospitalize ii appropriate
intervention such as ventricular assist	
device, intravenous vasopressor	
support or heart transplant indicated;	
ejection fraction < 20%	
*the event is considered resolved when	the patient is asymptomatic, has a resting ejection fraction
≥40% and ≤20% decrease from baseline	2 .
Cal	rdiac – QTc prolongation
Cardiac - prolonged QTc interval ≥	Refer to Table 9 Recommended dose modifications for
Grade 3 (QTcF > 500 msec	sonidegib.
or	Ç
>60 ms from	
baseline on at least 2 separate ECGs	
taken within 1 hour)	
	Other Cardiac Events
Grade 1	Maintain dose level
Grade 1	Maintain dose ievei
Grade 2	Implement 50% dose reduction of buparlisib
Grade 3	Omit dose and discontinue study drug
T 11 10 D	1 1 1 1 1 1 1 1 1 1 1 1 1 1 1 1 1 1 1 1
Table 10. Recommended dose modifications and dose delays for	
suspected dup	parlisib treatment-related toxicities
Worst toxicity CTCAE grade* (value)	During a cycle of therapy
-	
Grade 4	Omit dose and discontinue study drug
	Consider hospitalization if appropriate

Other	
Mood alteration	
* Mood questionnaire scores should be considered when assigning the AE Grade but psychiatric consult, if required, may determine the grade	

Grade 1	Maintain dose level

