Mild mood alteration (or Grade 2 anxiety if present at baseline)	Note : If question 9 (suicidal ideation) on the PHQ-9 has a positive response, or worsens in severity, the patient should be referred for psychiatric consult regardless of the total questionnaire score
Grade 2 Moderate mood alteration (for	Institute appropriate co-medication under the guidance of the psychiatrist. Maintain dose level.
Anxiety only, if worsened from baseline) and if there is no concurrent medical condition that accounts for an acute increase the PHQ score.	If the condition does not resolve to ≤ Grade 1 within 14 days despite medical treatment; then implement 50% dose reduction (continue to co-medicate) Note: If question 9 (suicidal ideation) on the PHQ-9 has a positive response, or worsens in severity, the patient should be referred for psychiatric consult regardless of the total questionnaire score
Grade 3	Discontinue study medication
Severe agitation; hospitalization not indicated	Note : If question 9 on the PHQ-9 has a positive response, or worsens in severity, the patient should be referred for psychiatric consult regardless of the total questionnaire score
Grade 4	Discontinue study medication. Consider hospitalization
Life-threatening consequences; urgent	if appropriate
intervention indicated	Note: If question 9 on the PHQ-9 has a positive response, or worsens in severity, the patient should be referred for psychiatric consult regardless of the total questionnaire score

Table 10. Recommended dose modifications and dose delays for suspected buparlisib treatment-related toxicities	
Worst toxicity	During a cycle of therapy
CTCAE grade* (value)	
Rash	
Grade 1 Macules /papules covering <10% BSA with or without symptoms (e.g. pruritus, burning)	Maintain dose level. Consider to initiate appropriate skin toxicity therapy (such as antihistamines, topical corticosteroids)

Grade 2 Macules/papules covering 10-30% BSA with or without symptoms; limiting instrumental ADLs	Reduce study drug dose to 50% of prior dose. Initiate/intensify appropriate skin toxicity therapy (such as antihistamines, topical corticosteroids)
Grade 3 Macules/papules covering >30% BSA with or without associated symptoms, limiting self-care ADLs	Discontinue study drug According to the investigators discretion, a paired skin biopsy could be obtained (from both an affected and an unaffected skin area for local histopathology assessment) if clinical appropriate

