4.1.2 Known Undesirable Side Effects of buparlisib

4.1.2.1 Neuropsychiatric events

In an ongoing phase 1a study of buparlisib in patients with solid tumors (CBKM120X2101), neuro-psychiatric adverse events, including reversible and generally mild to moderate mood alterations, described as anxiety, agitation with crying episodes and depression have been reported in patients treated with buparlisib. In this study, three out of five patients with moderate to severe mood alterations had a history of depression and/or anxiety. All patients with a documented medical history of depression/anxiety also developed mood alterations while treated with buparlisib at the 100 mg dose level and thus reflecting a potential risk group of patients.

In order to lower the risk of experiencing significant mood alterations within the proposed study, cancer patients with an active or history of major depressive episode, bipolar disorder, obsessive-compulsive disorder, schizophrenia, a history of suicide attempt or ideation, or homicide/homicidal ideation as judged by the investigator and/or based on recent psychiatric assessment will not qualify for study participation. Patients with corresponding symptoms CTCAE Grade ≥ 2 should immediately be examined by a psychiatrist and closely followed medically. Medical treatment with mood stabilizers (2^{nd} generation antipsychotics) such as olanzapine and quetiapine may be applied as per investigator's discretion and following consultation of a psychiatrist.

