4.1.2.1.1 Management of mood alteration

Patient self-rating mood questionnaires GAD-7 (anxiety) (see Table 11) and PHQ-9 (depression) (see Table 12) will be used:

- ◆◆ to support assessment of eligibility at Screening
- ◆◆ to monitor for newly occurring or worsening mood alterations during the study. The following grading system will be used for this study:

At Screening, a patient as judged by the investigator or who meets the cut-off score of ≥ 12 in the PHQ-9 or a cut-off of ≥ 15 in the GAD-7 mood scale, respectively, or select a positive response of '1, 2, or 3' to question number 9 regarding suicidal thoughts or ideation will be excluded from the study.

During the study, patients who meet the cut-off score of ≥ 10 (\geq CTCAE Grade 2 mood alteration) in either questionnaire or indicate a positive response by selecting '1, 2, or 3' to question number 9 on the PHQ-9 must see a psychiatrist for advice on the most appropriate medical treatment must see a psychiatrist for diagnosis and determination of most appropriate medical treatment. For anxiety, this applies only if status has worsened from baseline. Patients who experience \geq Grade 2 mood alteration will be followed by patient self-rating mood scale and will be seen weekly by the psychiatrist until resolved \leq Grade 1 or baseline (for anxiety), if there is no concurrent medical condition that accounts for an acute increase the PHQ score. Questionnaire responses will be checked by the psychiatrist at the weekly visits (until resolution to Grade 1 or baseline (for anxiety).

Table 11. GAD-7 anxiety scale

Over the last 2 weeks, how often have you been bothered by the following problems?	u Not at all	Several days	More than half the days	Nearly every day
(Use "./"to indicate your answer"				
1. Feeling nervous, anxious or on edge	0	1	2	3
2. Not being able to stop or control worrying	0	1	2	3
3. Worrying too much about different things	0	1	2	3
4. Trouble relaxing	0	1	2	3
5. Being so restless that it is hard to sit still	0	1	2	3
6. Becoming easily annoyed or irritable	0	1	2	3
7. Feeling afraid as if something awful might happen	0	1	2	3

Column totals:

= Total Score

If you checked off any problems, how difficult have these problems made it for you to do your work, take care of things at home, or get along with other people?

Not difficult at all

Somewhat difficult

Very

Difficult

Extremely

Difficult

Table 12. PHQ-9 depression scale

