Mood questionnaires will be scored according to Table 13 below.

Table 13. Toxicity grading based on mood questionnaire scores

	PH	Q-9	GAD-7		AD-7
Score	Severity	CTCAE grading	Score	Severity	CTCAE grading
0-4	None	Normal	0-4	None	Normal
5-9	Mild	Grade 1	5-9	Mild	Grade 1
10-19	Moderate	Grade 2	10-14	Moderate	Grade 2
20-27	Severe	Grade 3	≥ 15	Severe	Grade 3

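### After a positive PHQ-9 item 9, section 4.1.2.3.3 stops buparlisib, but Table 10 keeps the dose at Grades 1 and 2 and section 4.1.2.1.1 gives no hold

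*Combined protocol and SAP*

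**What the plan says.** Three places in the protocol act on a positive item 9 during treatment.

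- **Section 4.1.2.3.3** instructs staff to "omit treatment with buparlisib and refer the patient for psychiatric consultation". This applies "regardless of the total questionnaire score or CTCAE grading to confirm if study drug should be interrupted or permanently discontinued". The psychiatrist may then overrule the patient's self-report.
- **Section 4.1, Table 10, mood alteration.** The Grade 1 row keeps the dose unchanged. The Grade 2 row reads "Institute appropriate co-medication under the guidance of the psychiatrist. Maintain dose level", with a 50% reduction only if the event has not settled to Grade 1 or lower within 14 days. For a positive or worsening item 9, the note in both rows says "the patient should be referred for psychiatric consult regardless of the total questionnaire score". It says nothing about dose. Grades 3 and 4 discontinue study medication.
- **Section 4.1.2.1.1** says that a patient who gives a positive answer "to question number 9 on the PHQ-9 must see a psychiatrist for advice on the most appropriate medical treatment". It gives no dose instruction.

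On grading, section 4.1.2.1.1 states "Mood questionnaires will be scored according to Table 13 below". Table 10 qualifies this: "Mood questionnaire scores should be considered when assigning the AE Grade but psychiatric consult, if required, may determine the grade". On timing, section 4.1.2.1 says that patients with symptoms of Grade 2 or higher "should immediately be examined by a psychiatrist and closely followed medically". No equivalent is given for Grade 1.

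**The concern.** The same answer on the same form leads to opposite dosing instructions, depending on which page is open. Table 10 is where staff will look: section 4.1 presents it as the detailed source for buparlisib dose changes, and section 4.1.2.3.3 itself sends the reader there for psychiatric events. Because the table mentions item 9 by name, it appears complete. It also states an immediate hold where one is intended, for example for symptomatic Grade 2 and for Grade 3 hyperglycemia. Against that pattern, an unchanged dose plus referral reads as a decision not to hold.

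At stake is continued daily dosing of a drug with known mood effects in a patient who has just reported suicidal thoughts. The protocol treats this answer as serious elsewhere: at screening, a positive item 9 excludes the patient whatever the total score (section 3.2.2.2, criterion 6). Referral is required in all three places, so the gap is the dosing between the answer and the psychiatric assessment.

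**Working it through.** The plan gives no figure to reproduce here. The check compares the texts and then asks which scores fall in the conflicting rows.

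**Step 1. Immediate action on a positive item 9**

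| Grade of mood alteration | 4.1.2.3.3 | Table 10 | 4.1.2.1.1 |
|---|---|---|---|
| 1 | Omit buparlisib, refer | Keep dose, refer | Psychiatrist visit, dose not mentioned |
| 2 | Omit buparlisib, refer | Keep dose, co-medicate, refer; 50% reduction if unresolved at 14 days | Psychiatrist visit, dose not mentioned |
| 3 or 4 | Omit buparlisib, refer | Discontinue, refer | Psychiatrist visit, dose not mentioned |

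The instructions conflict at Grades 1 and 2. At Grades 3 and 4 both dosing texts stop drug.

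**Step 2. Which scores fall in those rows, if Table 13 sets the grade**

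Total = *a* + *S*, where *a* is the item 9 answer (1 to 3 if positive) and *S* is the sum of the other eight items (0 to 24). Table 13 gives 0–4 normal, 5–9 Grade 1, 10–19 Grade 2 and 20–27 Grade 3. Subtracting *a* from each limit gives the range of *S*:

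| Item 9 answer | Normal | Grade 1 | Grade 2 | Grade 3 |
|---|---|---|---|---|
| 1 | 0–3 | 4–8 | 9–18 | 19–24 |
| 2 | 0–2 | 3–7 | 8–17 | 18–24 |
| 3 | 0–1 | 2–6 | 7–16 | 17–24 |

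For the most severe item 9 answer, the Grade 3 threshold is 20 − 3 = 17. Any *S* from 2 to 16 puts that patient in a row that keeps the dose. In the normal column no Table 10 mood row applies, so only 4.1.2.3.3 and 4.1.2.1.1 reach the patient.

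**Step 3. Dosing during the gap**

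The buparlisib dose is 80 mg once daily (section 4.2.1), so a wait of *d* days means *d* doses. Read alone, the Grade 2 row makes no dose change for 14 days: 14 × 80 mg = 1,120 mg. Section 4.1.2.1 should shorten this, since it asks for immediate psychiatric examination at Grade 2. At Grade 1 no consult deadline is stated, so *d* has no stated limit.

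**Step 4. Where mood events fell in earlier studies**

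Table 7 (100 mg/day, any causality) sums as follows:

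- patients: 55 + 9 + 50 + 12 + 6 = 132
- mood disorders, all grades: 11 + 4 + 6 + 7 + 0 = 28
- Grade 3–4: 2 + 0 + 0 + 2 + 0 = 4

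So 28 − 4 = 24 of the 28 were below Grade 3. The dose differs from this study's, and these are not item 9 answers. The sum shows only that most recorded mood events lay in the grades where the texts disagree.

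**The case against.** The strongest reply is that 4.1.2.3.3 already settles the matter. It applies whatever the grade, Table 10 is organized by grade and headed as recommendations, and item 9 is marked as a special case with its own exit through the psychiatrist. On that reading only a cross-reference is missing. The wording does point to the hold as the overriding rule. But no sentence gives it precedence, and the table that staff dose from says the opposite at Grades 1 and 2.

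Second, 4.1.2.1.1 is silent on dose and can be followed together with the hold. That is right. The section does not order continued dosing; it fails to carry the hold. The direct contradiction is with Table 10.

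Third, 4.1.2.3.3 bases grading on clinical judgment under CTCAE, with the questionnaires as an aid, so a clinician may grade such a patient higher than the score implies. This stands, and the score ranges above are therefore conditional. Table 10 nevertheless places the item 9 note in its Grade 1 and Grade 2 rows, so it expects positive answers at those grades.

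Fourth, there are safeguards. Screening excludes patients with a history of suicidal ideation or a PHQ-9 total of 12 or more, the psychiatrist visit is mandatory, and section 4.3.5.5 repeats the questionnaires weekly in symptomatic patients. These lower the risk. None of them stops the drug while the consult is awaited.

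**Conclusion.** The inconsistency is real and should be corrected. Staff who follow the Grade 1 or Grade 2 mood row of Table 10 keep dosing a patient whom 4.1.2.3.3 takes off drug.

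The size can be stated per patient only: one 80 mg dose for each day between the answer and the psychiatric assessment. The statement that most score combinations fall below Grade 3 assumes that Table 13 sets the grade. The documents give no frequency of positive item 9 answers, so the number affected among the 24 planned patients cannot be estimated. The planned response-rate analysis is not affected; this is a matter of patient safety and consistent conduct.

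**What to change.** Add this sentence to the item 9 note in both the Grade 1 and Grade 2 mood rows of Table 10, and to section 4.1.2.1.1: *omit buparlisib pending psychiatric assessment, whatever the total score or CTCAE grade; this overrides the grade-based dose action*. Leave 4.1.2.3.3 unchanged. The addition to 4.1.2.1.1 is needed as well, because a patient with a positive item 9 and a total of 4 or less falls in no Table 10 mood row.

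The cost is some short interruptions in patients whom the psychiatrist later clears. The consult should be obtained well within 21 days: sections 4.1.1 and 4.2.1 take a patient off after a longer buparlisib delay, although section 4.1 lets a patient with clinical benefit continue after discussion with the drug supplier.
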